12.6 Sensitivity Analyses

We will perform several sensitivity analyses to assess the robustness of the results, particularly for the primary outcome. These include:

- i) Protocol-based analysis limited to participants who adhered to the protocol as described;
- ii) Competitive risk analysis: This analysis will treat death as a competitive risk factor for any outcome;
- iii) Missing data analysis: This analysis will assess the impact of missing data on the primary outcomes.
- iv) We will also conduct sensitivity analyses to account for any unforeseen issues that arise during the study process and that may affect the main conclusions.

12.7 Subgroup analyses

We will conduct several subgroup analyses to assess the consistency of effects across subgroups of participants:

- i. Age - Assumption that older participants will benefit more than younger ones.
- ii. Gender - Assumption that female participants will benefit more than male participants.
- iii. Vaccination status - Assumption that vaccinated participants will benefit more than unvaccinated participants.
- iv. Comorbidities at screening:
 - Obesity status (yes or no)
 - Cardiovascular disease (yes or no);
 - Lung disease (yes or no);

Our hypothesis is that participants with the clinical comorbidities described above will benefit more than those without these clinical conditions. All subgroup hypotheses are based on emerging data from other countries indicating the differential impact of COVID-19 by age, sex, vaccination status, and the presence of clinical comorbidities at baseline. Subgroup effects will be assessed by including an interaction term between the treatment group and the subgroup variables. These interaction effects will be exploratory in nature.

12.8 Missing Data

Due to the study design and short duration, we expect to obtain data from all participants. However, in the unlikely event of missing data, they will be addressed.

12.9 Policy on pooled analysis

It is expected that data from individual participants in similar studies may be pooled in a pooled analysis. De-identified data from the present study may be made available for these purposes following discussion by the Steering Committee and in accordance with a policy of academic-scientific cooperation to find solutions for the treatment of long COVID-19.

12.11 Summary table of analyses from the website

Result	Hypothesis	Outcome Measure	Statistical analysis method
Primary Mean score measured by the fatigue severity scale on day 60 after randomization	Drug treatment will be better than placebo	Fatigue Severity Scale	Bayesian Normal-Normal analysis
Secondary Mean score measured by the fatigue severity scale on day 30 after randomization	Drug treatment will be better than placebo	Fatigue Severity Scale	Bayesian Normal-Normal Analysis
Mean score measured by the fatigue severity scale on day 90 after randomization	Drug treatment will be better than placebo	Fatigue Severity Scale	Bayesian Normal-Normal Analysis
Health-related quality of life on day 60 after randomization	Drug treatment will be better than placebo		Bayesian Normal-Normal Analysis
All-cause mortality by day 60 after randomization	Treatment will prevent overall mortality	Measuring deaths in the groups	Logistic regression
Time to all-cause mortality up to day 60 after randomization	The treatment will prevent overall mortality	Interval in days between randomization and mortality	Cox regression
Unexpected hospitalization from any cause by day 60 after randomization	The treatment will prevent hospitalization	Measurement of deaths in the groups	Logistic regression
Unexpected hospitalization for any cause up to day 60 after randomization	The treatment will prevent hospitalization	Interval in days between randomization and mortality	Cox regression
Safety of the IP	The drugs are safe in participants with long COVID	Measurement of adverse events in treatment groups	Descriptive analysis
3) Subgroup analysis: i) Age (young vs. elderly) (ii) Sex (male vs. female) female)	Older adults are at higher risk of complications Men are at higher risk	Risk assessment	Regression methods with appropriate interaction terms.

iv) Vaccination status	Unvaccinated individuals are at higher risk		
v) Obesity	Obesity carries a higher risk		
vi) Diabetes	Diabetes carries a higher risk		
vii) Hypertension			
viii) Cardiovascular disease	People with high blood pressure are at higher risk		
ix) Chronic lung disease	Lung disease carries a higher risk		
4) Sensitivity analysis	The results remain robust	Primary and key secondary outcomes (fatigue score at day 30 and day 60)	

IMPORTANT NOTES:
 
 In all analyses, results will be expressed as estimated effects with corresponding 95% uncertainty estimates 			

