5.2 Inclusion Criteria

Participants must meet all of the following criteria to be eligible for participation in this study:

1. Age 18 years or older at the time of screening.
2. Willing and able to provide written informed consent, or have a legal representative who can provide informed consent (where approved locally and nationally).
3. A previous confirmed case of SARS-CoV-2 infection (e.g., reports having had a positive nucleic acid amplification test or a positive professional-use or self-test SARS-CoV-2 rapid antigen test).
4. Participants with clinical symptoms consistent with LONG COVID according to international definitions: (www.nice.org.uk/guidance/ng188), (https://www.who.int/publications/i/item/WHO-2019-nCoV-Post_COVID-19_condition-Clinical_case_definition-2021.1), and fatigue symptoms with an average score of at least 03 on the Fatigue Severity Scale (FSS);
5. Have a diagnosis of the most recent episode of COVID-19 within 24 months of the screening visit date.
6. Not currently hospitalized or in need of hospitalization, or having been hospitalized in an intensive care unit during the COVID-19 episode.
7. Participants with the following vital signs:
 - a. Heart rate between 55 and 100 bpm;
 - b. Temperature below 38°C;
 - c. Oxygen saturation \geq 95%.
8. Participants who are capable of becoming pregnant or whose partners are capable of becoming pregnant must agree to use appropriate contraceptive methods during the study and for up to 90 days of follow-up.
9. Symptoms of fatigue cannot be attributed to another cause (in the researcher's opinion).
10. Willingness to follow all study procedures.

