12.3 Sample Size Calculation I

The sample size of 500 participants per arm and its operational characteristics were confirmed using closed-form, analytical, and numerical methods. The operational characteristics for the head-to-head comparison of the treatment arm versus the placebo arm in reducing the mean fatigue score measured by the Fatigue Severity Scale (1 to 9) on day 60 are shown in Table 2. For each pairwise comparison against the placebo arm, the Type I error rate (alpha) was set at 0.025 (one-sided) using a Bayesian normal-normal model. For the planning of our study, we assumed a plausible standard deviation value of 1.7, which was estimated from a recent study that evaluated the psychometric properties of the fatigue severity scale in participants recovering from COVID-19.¹

Table 2 : Simulated operational characteristics of our study for varying sample sizes

Dropout rate	Reduction in FSS score	Sample (n = 252)	Sample (n = 500)	Sample (n = 752)	Sample (n = 1000)
0.0	0.00	2.5%	2.5%	2.5%	2.5%
	0.15	13.2%	22.6%	32.3%	41.5%
	0.30	41.8%	71.2%	87.8%	95.2%

Dropout rate	Reduction in FSS score	Sample (n = 252)	Sample (n = 500)	Sample (n = 752)	Sample (n = 1000)
	0.45	76.8%	97.1%	99.7%	100.0%
2.5	0.00	2.5%	2.5%	2.5%	2.5%
	0.15	12.9%	22.0%	31.5%	40.5%
	0.30	40.6%	69.7%	86.8%	94.7%
	0.45	75.4%	96.6%	99.7%	100.0%
5.0	0.00	2.5%	2.5%	2.5%	2.5%
	0.15	12.6%	21.6%	30.8%	39.6%
	0.30	39.5%	68.5%	85.9%	94.1%
	0.45	73.9%	96.3%	99.6%	100.0%
10.0	0.00	2.5%	2.5%	2.5%	2.5%
	0.15	12.2%	20.6%	29.4%	37.8%
	0.30	37.7%	66.1%	84.0%	92.9%
	0.45	71.5%	95.4%	99.4%	99.9%

Thus, the clinical trial will recruit 1,500 participants, divided into three groups of 500 participants each. With the proposed sample size of 500 participants in each group, the study will have adequate statistical power to detect a clinically significant treatment effect. A difference of 0.45 has been suggested as the minimum clinically important difference (MID) on the fatigue severity scale in population groups of participants with multiple sclerosis and chronic fatigue.² Even with a 10% dropout rate, our estimated power to detect a difference of 0.45 is above 90%.

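### The exploratory treatment-by-age interaction is set up on a two-level age variable, which loses information if the drug effect changes gradually with age

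*Protocol*

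**What the plan says.** Section 12.11 of the Protocol gives the age subgroup variable as "Age (young vs. elderly") and the method for the subgroup block as "Regression methods with appropriate interaction terms". Section 12.7 says how the subgroup variables are used: "Subgroup effects will be assessed by including an interaction term between the treatment group and the subgroup variables". It also gives the tests their status: "These interaction effects will be exploratory in nature". The age hypothesis in 12.7 is "Assumption that older participants will benefit more than younger ones", with no age boundary attached.

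The inclusion criteria in section 5.2 admit anyone meeting "Age 18 years or older at the time of screening", with no upper limit. Baseline procedures (4.1.1 and 8.2) include demographic data, and the inclusion criterion cannot be applied without knowing each participant's age. The protocol states no mean, SD or expected share of elderly participants, and no reason for dividing age in two.

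**The concern.** A two-level age variable treats everyone on the same side of the cut as interchangeable. If the drug effect rises or falls gradually with age, the differences within each side carry information about that change, and the split discards it. The loss grows as the elderly group becomes smaller.

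Tests of interaction are weak to begin with. At stake is how the exploratory age result is read. A null result from a split could be taken as evidence that the effect is consistent across ages when the test had little chance of showing otherwise, and a positive result could depend on where the cut was placed.

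**Working it through.** **The plan's own figures.** The protocol states no figure for the age interaction. The inputs can be checked against Table 2 in section 12.3, which gives 22.6%, 71.2% and 97.1% power at n = 500 for FSS differences of 0.15, 0.30 and 0.45. A fixed design with 500 per arm, SD 1.7 and one-sided 0.025 gives 28.6%, 79.7% and 98.7%. Four looks (25%, 50%, 75%, 100%) with a constant boundary of z about 2.365 give 22.6%, 71.5% and 97.3%. Table 2 is therefore consistent with n per arm and a design with interim looks. Reading n as the two-arm total gives 16.5%, 50.5% and 84.1%, which does not fit.

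**Inputs from the protocol (12.3).** There are 500 participants per arm. On variability, "we assumed a plausible standard deviation value of 1.7". On error rate, "the Type I error rate (alpha) was set at 0.025 (one-sided) using a Bayesian normal-normal model", which has the same critical value, 1.96, as a two-sided 5% test.

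**Inputs that are assumptions.** These are the shape of the age distribution, the share p classed as elderly, a linear change of effect with age, and the size of that change.

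**Step 1: information kept.** For a linear treatment-by-age interaction, a split keeps the squared correlation between age and the elderly indicator.

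- Normal age: φ(z_p)² / [p(1 − p)], where z_p is the normal quantile with upper tail p.
- Uniform age: 3p(1 − p).

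| Share elderly | Normal: kept | Normal: lost | Uniform: kept | Uniform: lost |
|---|---|---|---|---|
| 50% | 0.637 | 36% | 0.75 | 25% |
| 20% | 0.490 | 51% | 0.48 | 52% |
| 10% | 0.342 | 66% | 0.27 | 73% |

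For example, at p = 0.5 with normal age, 0.3989² / 0.25 = 0.637. In a comparison of 1,000 participants (one drug arm and placebo), the normal-age losses are like discarding 360 to 660 of them for this test, and the uniform-age losses like discarding 250 to 730.

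Two checks on the range:

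- Normal age truncated at 18, with assumed means of 45 to 55 and SDs of 14 to 15, loses about 34% to 68% for cuts from the median up to 65 years.
- If only 5% are elderly, the loss is 78% for normal age and 86% for uniform age.

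**Step 2: what this means for power.** Take age in SD units. The standard error of the interaction slope is 1.7 × √(2/500) = 0.1075. This is a fixed-design calculation without dropout, for normal age.

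- Assumed slope of 0.30 FSS points per SD of age: z = 0.30 / 0.1075 = 2.79 with age in years. Multiplying by the square root of the information kept gives 2.23, 1.95 and 1.63 for the splits.
- Assumed slope of 0.15: z = 0.15 / 0.1075 = 1.40 with age in years, and 1.11, 0.98 and 0.82 for the splits.

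| Assumed slope | Age in years | 50% elderly | 20% elderly | 10% elderly |
|---|---|---|---|---|
| 0.30 per SD | 80% | 60% | 50% | 37% |
| 0.15 per SD | 29% | 20% | 16% | 13% |

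The share of information lost in Step 1 does not depend on the slope. The gap in power does.

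**The case against.** **The split is only lightly fixed.** It appears as a parenthetical label in a summary table, while 12.7 names age without categories, and the protocol defers detail to an analysis plan that is not shown. This stands in part. The absence of a cut-point is not a fault, because it may be set in the SAP. But the two-level form is stated, 12.7 feeds the subgroup variables into the interaction, and no choice of cut removes the loss if the change is gradual.

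**The hypothesis is not a trend.** A reader might infer from 12.7 that the protocol posits a steady change with age. It does not: it gives a direction between older and younger participants and no shape. Linearity is an assumption of this review. If the effect really changes in a step at the cut, a split is the right model and loses little or nothing.

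**The illustrative slope is large.** A slope of 0.30 per SD means that the drug effect differs by 0.60 points between participants one SD below and one SD above the mean age, which exceeds the 0.45 difference used for planning in 12.3. This stands. At 0.15 per SD the test is underpowered however age is coded, and the gain from age in years is 9 to 16 percentage points.

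**The table row is not clearly about the FSS.** Its hypothesis cell concerns the risk of complications and its outcome cell concerns risk. This stands as a limit on the power example, which applies the test to the FSS score on the strength of 12.7. The information loss in Step 1 comes from how age is coded and does not use the FSS SD.

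**Categorical age subgroups are a common way to report.** They are, and the fix keeps them for that purpose. The point concerns only the variable used in the test.

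**Conclusion.** The point holds in a conditional form and is minor. As written, 12.11 and 12.7 test effect modification by age on a two-level variable without a stated reason, although a more informative variable is at hand. If modification is roughly linear and between 10% and 50% of participants are classed as elderly, the loss is about 36% to 66% of the information for normal age and 25% to 73% for uniform age. It can be larger with very few elderly participants and close to zero for a step at the cut.

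Two stronger readings are tempting. The first is that the split discards a third to two thirds of the information as a matter of fact. The protocol gives no age distribution, cut or shape of effect, so no unconditional figure can be drawn from it. The second is that the trial's conclusions are weakened. The interaction tests are declared exploratory, and the primary analysis, sample size and error control do not depend on them.

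**What to change.** In 12.11, replace the two-level age entry with age in years, and say in 12.7 that the treatment-by-age interaction is tested with a linear term for age, with a spline as a check on shape. Keep age categories for display in the forest plot only, and keep the test exploratory.

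The cost is a change of wording in the two sections and in the SAP. No new data are needed.

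This does not settle a separate inconsistency in the same analysis: the Protocol Overview expects younger participants to benefit more, while 12.7 expects older ones to. The direction should be reconciled in the same edit.

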13 ETHICAL CONSIDERATIONS OF THE STUDY

13.1 *Ethical conduct of the study*

The study will be conducted in accordance with the principles of the World Medical Association's Declaration of Helsinki²²⁹ and the International Council for Harmonisation (ICH) guidelines for Good Clinical Practice (GCP), as amended.

The investigator must ensure the anonymity of all study participants. Each participant must be assigned a unique participant number, which must be used on all forms associated with the participant's documents or samples that will be provided to the sponsor or any party performing tests on behalf of the sponsor (e.g., blood for central laboratory testing).

All anonymous data remain the property of the Steering Committee.

13.2 *Informed consent*

The participants' individual medical information obtained as a result of this study is considered confidential, and its disclosure to unauthorized persons is prohibited. Participant confidentiality will be ensured by using unique participant numbers instead of names. If the results of this study are reported in medical journals or at meetings, or if they are submitted to the appropriate regulatory authorities in connection with regulatory procedures, such as applications for marketing authorization of pharmaceutical products, the participant's identity will not be disclosed.

With the participant's permission, medical information may be provided to the participant's personal physician or other appropriate medical staff responsible for the participant's well-being.

In accordance with GCP guidelines, all participants will be informed about the purpose of the research, the possible risks, and their right to withdraw from the study at any time, without any harm and without risk to their future medical care at the center. Each participant must agree to cooperate in all aspects of the study and must provide written confirmation (signed informed consent form) to the investigator prior to participation in the study. If the informed consent form is modified during the course of the study, active participants must sign the new version to continue participating in the study. For any updated or revised ICF, if applicable, the participant record must state that written informed consent was obtained for the use of the updated/revised consent form for continued participation in the clinical study. The ICF must be revised whenever there are changes to the

procedures in the protocol amendment associated with the ICF procedures or when new information becomes available that may affect the participant's willingness to participate. Each participant will receive a copy of each version of the form that they sign before and during the study.

Informed consent may be obtained in electronic format, with a copy made available to the participant. In this situation, the Ethics Committee must approve the step-by-step procedure to be adopted in the process of obtaining informed consent, which must be approved in advance so that this method may be adopted by participating centers.

No participant should participate in study activities until informed consent has been obtained. Documentation of the informed consent process and the discussion of the information provided to the participant must be included in the participant's medical record and include a statement that informed consent was obtained prior to participation in the study. Signed forms (ICFs) must remain in the participant's files and must be available for review by monitors, auditors, and/or inspectors from regulatory agencies at any time.

13.3 Research Ethics Committee (CEP)

All researchers participating in this study must be governed by an appropriate REC. The REC/CONEP system must review and approve this protocol, the TCLE, the study documents, and any information to be provided to the participant before a site may begin conducting any study-related activities.

Subsequently, the investigator is responsible for obtaining renewed approval from the CEP annually, or more frequently, in accordance with regulatory requirements and the policies and procedures established by the CEP. Copies of the investigator's annual report and other reports required to be submitted to the CEP, as well as copies of the CEP's ongoing approval, must be provided to the Steering Committee. The investigator must also inform the REC of any protocol changes or amendments, expedited SAE reports submitted to regulatory authorities, and other significant safety concerns, in accordance with the IRB policy. Written documentation of the IRB's approval of protocol amendments must be received prior to their implementation. Upon completion or termination of the study, investigators must notify their IRBs. The investigator shall comply with IRB policies throughout the study period.

14 QUALITY CONTROL AND QUALITY ASSURANCE

The integrity and quality of participant data will be ensured through training and instruction on the completion of clinical records, quality control checks, ongoing analysis of clinical data (including medical history and safety reviews), and verification and reconciliation of source data.

The investigator will also allow the Steering Committee or its audit representative, the CEP, ANVISA, or other regulatory authority inspectors to review and inspect the facilities, procedures, and all records relevant to this study. These records include, among others, the informed consent form signed by the participant, source documentation, regulatory and essential documents, clinical records, and drug accounting records.

The following measures will be taken to ensure that the study is conducted by the research center in accordance with the study protocol, GCP, and other applicable regulatory requirements:

- Meeting with the investigator
- Site Initiation Visit
- Routine monitoring of the study and the research center, if applicable
- Training on the protocol and documented GCP
- Review of medical records and questionnaires against source documents
- Collection of normal reference ranges from the local laboratory

14.1 *Quality management: critical processes and data*

The following processes and data were identified during the risk management activities for this study as essential to ensuring the protection of human participants and the reliability of the study results.

Throughout the study, the clinical study team will work to ensure that the clinical study is operationally feasible, focusing on the study and on activities essential to the protection of human participants and the reliability of the study results, including, but not limited to, the following:

Design and implementation of the study protocol.

Tools and procedures for collecting and processing supporting data.

Tools and procedures to ensure the rights and protection of research participants.

Activities essential for study decision-making and adherence.

15 REPORTING AND DATA RECORDING

Source documents are original documents, data, and records (e.g., case histories, physician progress notes, nursing notes, medical records, hospital records, clinical and office charts, laboratory notes, evaluation memos or checklists, pharmacy dispensing records, automated instrument data records, certified copies or transcripts after verification as accurate and complete, records maintained in the pharmacy or laboratories, and participant records). Source data are contained in the source documents and must be sufficient to reconstruct all data transcribed into clinical records and to evaluate the study. Examples of source data include clinical findings, observations, summaries of inclusion information and RCT procedures, assessment of the clinical significance of laboratory results, severity and intensity of AEs, and the investigator's judgment regarding the relationship of AEs to study medications.

The investigator must prepare and maintain adequate and accurate case records that document all observations and other data relevant to the investigation for all participants.

Source documentation must be available during the monitoring visit to verify the data entered in the eCRFs, as necessary. Source documentation must also be available for verification by auditors and/or inspectors, as necessary.

15.1 *Documentation source*

The investigator must maintain adequate and accurate source documents on which the case reports for each participant are based. They must be separate and distinguishable. These records must include detailed notes on:

- The medical history prior to study participation;
- Basic identifying information, such as demographic data, that links the participant's source documents;
- The results of all diagnostic tests performed, diagnoses made, therapy provided, and any other data regarding the participant's medical condition;
- The participant's exposure to the study treatment;
- All AEs and pregnancies;
- All special circumstances;
- The participant's exposure to any concomitant therapy;

- All relevant observations and data regarding the participant's clinical condition during the study;
- Verbal and written communication with the participant regarding the study treatment (including the risks and benefits of the study); the date of informed consent must be recorded in the source documentation.

All study data must be available in the source documentation.

